1.0 Study Summary

1.1

Study Title	Doxy.me VR vs. Telemental Health-Based Exposure Therapy
Study Design	Feasibility randomized controlled efficacy trial
Primary Objective/Purpose	Assess the feasibility of conducting a randomized controlled efficacy trial comparing the delivery of exposure therapy via a telemedicine-based virtual reality clinic (Doxy.me VR) vs. standard telemental health (TMH) to adults with intense fear of dogs, snakes, and/or spiders.
Secondary Objective(s)/Purposes	Preliminarily examine the efficacy of using Doxy.me VR vs. TMH in reducing phobia severity.
Research Intervention(s)	Exposure Therapy
ClinicalTrials.gov NCT #	Registration on clinicaltrials.gov is pending
Study Population	Adults (≥ 18 years old) with intense fear of dogs, snakes, and/or spiders.
Sample Size	30
Study Duration for individual subjects	In total, participants will spend approximately 38 hours over 13 study visits (12 Therapy and 1 Baseline Assessment) engaging in study procedures over the course of three months.
Study Specific Abbreviations/ Definitions	telemedicine-based virtual reality clinic (Doxy.me VR); standard telemental health (TMH); Virtual Reality (VR); Cognitive Behavioral Therapy (CBT)

2.0 Objectives

2.1 Primary Objective: Assess the feasibility of conducting a randomized controlled efficacy trial comparing the delivery of exposure therapy via a telemedicine-based virtual reality clinic (Doxy.me VR) vs. standard telemental health (TMH) to adults with intense fear of dogs, snakes, and/or spiders.

Secondary Objective: Preliminarily examine the efficacy of using Doxy.me VR vs. TMH in reducing phobia severity.

2.2 This is a feasibility trial and not powered for hypothesis testing.

3.0 Background

3.1 Telemedicine revolutionized mental health services (i.e., telemental health) by bringing accessible and personalized treatment at a distance.(Bunnell, [name], et al., 2020; Bunnell, Sprague, et al., 2020). Telemental health is equally to more effective than in-person care with higher patient satisfaction at reduced costs.(Adams et al., 2018; Flodgren et al., 2015; Hilty et al., 2013; Langarizadeh et al., 2017; Yuen et al., 2012) Further, telemedicine transcends socio-cultural (e.g., stigma) and geographic (e.g., transportation) barriers that have traditionally limited access and use of mental health services.(Baker et al., 2011; Rojas & Gagnon, 2008; Wootton et al., 2011) Telemedicine has become the standard of modern mental health care with 85% of all mental health services in the U.S. now delivered remotely, a trend that is fully expected to continue post-pandemic.(Doran & Lawson, 2021; Khan et al., 2020; Nguyen et al., 2020; Pierce et al., 2020) As telemedicine evolves, innovative solutions that enhance telemedicine utility and outcomes will be needed for providers to continue delivering state-of-the-art telemental health care.(Bunnell, [name], et al., 2020)

Virtual reality (VR) uses interactive and immersive simulation to facilitate mental health therapies.(Maples-Keller et al., 2017) Stressors that are physical (e.g., phobias, trauma, addiction) or psychological (e.g., body image, mood, identity) can be realistically recreated in VR for safe, repeatable, and effective therapy.(Jerdan et al., 2018; Maples-Keller et al., 2017; Srivastava et al., 2014) VR is engaging and improves treatment compliance and retention, making VR conducive to the vital practice of in- and between-session mental health exercises.(Bell et al., 2020) There is abundant support for VR mental health therapy in on-site settings.(Park et al., 2019; Pimentel et al., 2021) However, VR mental health therapy via telemedicine is limited to preliminary efficacy studies.(Dilgul et al., 2021; Goldenhersch et al., 2020; Tamplin et al., 2020) There is strong potential to combine the accessibility of telemedicine and clinical utility of VR as the next evolution of telemental health care.

With this goal, Doxy.me Inc. partnered with the University of South Florida to create Doxy.me VR is a standalone app currently available on Quest 2 headsets via invite only. The app is designed for a therapist to meet with a client in a private, comfortable VR clinic office. To join each other in VR, the therapist selects a room code and provides that code to their client, who joins by entering that code into the app. While joined in the same VR room, the therapist and client can interact by speaking with each other in

immersive VR. Therapists can also spawn a variety of small animals such as dogs, snakes, and spiders for use in treating specific phobias. Therapists can browse, select, maneuver, remove, and choose animations for the animals to exhibit once made visible to the client.

[figure not shown]

Figure 1. Screenshots of Doxy.me Virtual Reality clinic with stimuli

3.2 N/A

4.0 Study Intervention

4.1 This study aims to assess the feasibility of conducting a randomized controlled efficacy trial comparing the delivery of exposure therapy via a telemedicine-based virtual reality clinic (Doxy.me VR) vs. standard telemental health (TMH) to adults with intense fear of dogs, snakes, and/or spiders. Exposure therapy is a gold standard treatment for phobias and other anxiety-related mental health disorders (Taylor, 2003). Exposure therapy is acceptable, efficient, and produces durable effects (Vinograd & Craske, 2020). By exposing an individual to their fear-related stimuli (e.g., dog) in a controlled setting (e.g., therapist's office), the individual's fear response diminishes as their anxiety reduces over prolonged and repeated exposure (e.g., the individual is no longer fearful around dogs). The most common approach to this process includes gradual exposure which

begins with less intense stimuli and increases in intensity over time. One way to do gradual exposure is multimedia stimuli (e.g., photos, videos) and then gradually moving towards exposure to real life stimuli (i.e., in-vivo exposure). Another way is using VR stimuli in which patients are immersed in a virtual environment and interact with virtual stimuli (i.e., in virtual exposure). VR-based exposure therapy is a safe, accessible, and engaging alternative to in-vivo exposure therapy that can be less stressful and more conducive to treatment success (Horigome et al., 2020; Meyerbröker & Emmelkamp, 2010; Parsons & Rizzo, 2008; Yoshinaga et al., 2020).

The present study will use an exposure therapy protocol developed specifically for Virtual Reality (Stephane Bouchard et al., 2012; Côté & Bouchard, 2005; Michalyszyn et al., 2010; St-Jacques et al., 2010). Following the baseline assessment session (Study Visit 1), the treatment is comprised of 12, \leq 60-minute therapy sessions: one psychoeducation and treatment planning session, 10 exposure sessions, and one relapse prevention session (Study Visits 2-13). During the first therapy session, patients learn about the principles of Cognitive Behavioral Therapy (CBT), what causes anxiety and specific phobias, procedures for exposure, and complete a fear hierarchy, which is a list of situations ranked from least to most anxiety provoking. These lists will include a text-based list of various virtual/multimedia situations (i.e., static, and active states of different types of feared animals) and 'in vivo'/live situations (e.g., petting a dog, touching a snake at a pet store). Therapy sessions 2-11 begin with a review of homework followed by a ~35-minute virtual exposure session. Patients report their anxiety level using a 1-100% scale on a 5-minute interval throughout the exposure and remain in the exposure until they report a 50% reduction in their anxiety rating following the introduction of the stimulus. Upon completion of the exposure, the study therapist (i.e., a Postdoctoral Fellow and Clinical Psychologist) and patient process thoughts and feelings related to the exposure, reframe appraisals of their feared stimuli through cognitive restructuring, and practice breathing retraining and relaxation methods. The Doxy.me VR group will conduct their in-session exposures in the VR clinic and the TMH group will conduct their in-session exposures using multimedia on the Doxy.me platform (e.g., screen sharing videos and photos). This intervention requires daily homework practicing virtual exposures conducted in session and eventually progressing to in vivo exposures. Once patients have progressed through all virtual situations in their hierarchy and have completed their first in vivo exposure for homework, weekly therapy sessions will be devoting to processing between-session in vivo exposures and will last approximately 45 minutes. See Treatment Manual in Local Site Documents for a more detailed outline of the intervention.

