Participants will receive weekly ≤ 60 -minute therapy sessions (see Section 4.0 Study Intervention). Therapy session visits will be scheduled using Microsoft Bookings and participants will receive a calendar invitation and email reminders 24 hours and 1 hour prior to the scheduled visit time (See Appointment invitations and reminders in Local Site Documents). All therapy sessions will be conducted via videoconferencing, with the Doxy.me VR group transitioning to the Doxy.me VR clinic for the exposure exercise portion of the session. Participants in this group will be mailed a Meta Quest 2 VR headset with the Doxy.me VR app pre-loaded on the device. This headset will be owned by the University of South Florida and will be required to be returned when participants complete the study. Postage will be covered by the study. All therapy sessions will include the assignment of homework, including reading an informational handout after therapy session 1 and exposure therapy assignments after therapy sessions 2-11. Daily exposure-based homework assignments will require participants to practice the same exposure exercises they completed during that week's therapy session for a minimum of 30 minutes, with the specific situation being assigned to participants by the study therapist (i.e., Postdoctoral Fellow). Participants will receive text/email reminders with links to REDCap surveys that will provide instructions for the homework assignment, including situation to be used in the exposure exercise, and ask participants to report the results of the homework exercise including anxiety levels during the exposure exercise (see Treatment Data Collection Forms in Local Site Documents). At the end of each therapy session the study therapist (i.e., Postdoctoral Fellow) will send participants a link via the videoconference platforms messaging feature to a REDCap survey with the weekly assessment, which participants will be asked to complete before the end of the therapy session (see Measures in Local Site Documents and Figure 2. Study Schema and Schedule of Events). Therapy sessions will be audio recorded and 20% of recordings will be observed by the PI to rate fidelity to the protocol. All therapy session notes will be completed and stored in REDCap and signed by both the therapist (i.e., Postdoctoral Fellow) and supervisor (PI).

Assessment Strategy and Measures

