All trial assessments are listed in Table 1 and were chosen considering several factors including (1) sound psychometric properties, (2) ease of administration, (3) past use in similar clinical trials, and (4) brevity. All questionnaires will be completed via REDCap

survey with study staff present via videoconference to answer any questions (see Measures in Local Site Documents and Figure 2. Study Schema and Schedule of Events).

[figure not shown]
Table 1. Study Assessments

[figure not shown]
Domain	Informant	Measure
Demographics	Patient	Patient Demographics Questionnaire
Anxiety Severity	Patient	General Anxiety Disorder-7 (GAD-7)(Johnson et al., 2019; Spitzer et al., 2006)
Depression Severity	Patient	Patient Health Questionnaire-9 (PHQ-9)(Kroenke et al., 2011, 2009)
Therapeutic Alliance	Patient Provider	Working Alliance Inventory- Short Revised (WAI-SR)(Hatcher & Gillasp, 2006) Working Alliance Inventory – Short Revised Therapist (WAI-SRT; (Hatcher & Gillasp, 2006)
Treatment Satisfaction	Patient	Client Satisfaction Questionnaire (CSQ-8)(Larsen et al., 1979)
Specific Phobia Severity	Patient	Severity Measure for Specific Phobia-Adult (SMSP-A; (Craske et al., 2013);
Specific Phobia Diagnosis	Patient	Diagnostic Assessment Research Tool (DART;(Schneider et al., 2022)
Presence	Patient	Single Item Presence Questionnaire (SIPQ; (S. Bouchard et al., 2005)
Cybersickness	Patient	Cybersickness in Virtual Reality Questionnaire (CSQ-VR; (Kourtesis et al., 2023)
Usability	Patient	System Usability Scale (Peres et al., 2013)

Treatment Fidelity

All treatment sessions will be recorded and 20% will be rated by the Supervisor (PI) using a Treatment Fidelity Checklist based on the treatment manual (see Treatment Data Collection Forms in Local Site Documents).

Figure 2. Study Schema and Schedule of Events

5.3 There are no procedures or interventions that are going to be conducted as part of this research project that would have been conducted even if the research was not occurring. We are conducting the procedures solely for research purposes.

5.4 There are no additional foreseeable risks to the above procedures in need of further mitigation beyond those ordinarily incurred in working with this population. Standard operational procedures of the USF Department of Psychiatry and Behavioral Neurosciences specify responsibilities for handling dangers to self and others, safety planning, and mandatory reporting responsibilities.

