14.0 Risks to Subjects

14.1 Physical, psychological, social, cultural, financial, and legal risks, and risks to privacy and/or confidentiality associated with this research are minimal because the probability and magnitude of harm or discomfort anticipated in the proposed research are not greater, in and of themselves, than those ordinarily encountered in daily lives of the general population or during the performance of routine physical or psychological examinations or tests.

These minimal risks include:

1. Possible breach of participant privacy and/or confidentiality
2. Possible breach of the security of participant online data
3. Possible participant discomfort due to completing psychological questionnaires and assessments
4. Possible participant discomfort due to having therapy sessions recorded
5. Participant discomfort during exposure therapy exercises. This discomfort is temporary but necessary for treatment gains to occur.
6. Possible participant discomfort or cybersickness as a result of using the VR system, the duration of which is typically 5-10 minutes, and which will be assessed following each VR-based exposure using the CSQ-VR.
7. Possible disclosure of suicidality or homicidality requiring mandatory reporting if participants are at imminent risk of endangering themselves or others. Standard operational procedures of the USF Department of Psychiatry and Behavioral Neurosciences specify responsibilities for handling dangers to self and others, safety planning, and mandatory reporting responsibilities.

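### Both arms do between-session homework with live animals, yet animal injury is not a listed risk, no adverse-event collection is stated, and the only side-effect instrument follows VR exposures

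*Protocol*

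**What the plan says.** Section 4.0 has every patient build a fear hierarchy that mixes virtual or multimedia situations with live ones, for example "petting a dog, touching a snake at a pet store". It separates the arms only for the in-session exposure (VR clinic or shared multimedia). It then says of the treatment as a whole: "This intervention requires daily homework practicing virtual exposures conducted in session and eventually progressing to in vivo exposures". Once the first live homework is done, "weekly therapy sessions will be devoting to processing between-session in vivo exposures". Under Section 5.0 (Treatment), the VR arm is also mailed a headset for use at home.

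Section 14.1 rates the risks as minimal, "not greater, in and of themselves, than those ordinarily encountered in daily lives of the general population", and names seven. Section 5.4 says: "There are no additional foreseeable risks to the above procedures in need of further mitigation beyond those ordinarily incurred" in work with this population, and refers to departmental procedures on danger to self and others.

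On collection, Section 14.1 says of cybersickness "which will be assessed following each VR-based exposure using the CSQ-VR". Section 5.0 says the homework surveys "ask participants to report the results of the homework exercise including anxiety levels during the exposure exercise". Section 17.1 deals with distress and referral. Sections 17.2 and 19.1 are marked N/A.

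**The concern.** The protocol sends participants in both arms to handle or approach live animals, and one arm to move about at home in a headset. Neither the risk list nor the mitigation statement mentions the physical harm that could follow, and no section says how such harm would be asked about or recorded. Meanwhile one side effect, cybersickness, is sought repeatedly, but only after VR exposures.

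Two things are at stake. First, physical harm from the step both arms share could go unrecorded in a trial meant to prepare a larger one. Second, anyone who describes side effects by arm would set a structured record in VR beside no counterpart in TMH. A difference could then come from who was asked, and not from what happened.

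**Working it through.** The protocol gives no figure to reproduce, so the check sets its sections side by side.

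**1. Who does live homework?** The sentence in Section 4.0 that separates the arms concerns in-session exposure only. The homework sentence that follows covers the intervention, so both arms progress to live animals. The exposures take place between sessions. That no therapist is present is a fair inference, but the text does not say so.

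**2. What do the seven risks in Section 14.1 cover?** They are: privacy; online data security; discomfort with questionnaires; discomfort with recording; discomfort in exposure exercises; discomfort or cybersickness from the VR system; and disclosure of suicidality or homicidality.
- Risks naming a bite, scratch, allergic reaction or other animal injury: 0 of 7.
- Risks naming a fall or collision in the headset: 0 of 7.
- The nearest entries describe temporary discomfort (exposure) and discomfort or cybersickness (VR).

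**3. Which channels are stated, and for whom?**

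| Channel | Arm | What it is stated to capture |
|---|---|---|
| CSQ-VR (Table 1, 14.1) | VR exposures only | Cybersickness |
| DART Risk Assessment Module (5.0, 9.2, 9.3) | Both | Suicidal or homicidal intent or plan |
| GAD-7, PHQ-9, SMSP-A (Table 1) | Not limited to an arm | Anxiety, depression, phobia severity |
| Homework REDCap survey (5.0) | Both | Homework results, anxiety levels |
| Homework review, sessions 2-11 (4.0) | Both | Unstructured discussion |
| Safety monitoring (17.1) | Both | Distress, referral |

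No row names injury or adverse events in general.

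**4. How uneven is the one side-effect instrument?** Therapy sessions 2 to 11 make 11 − 2 + 1 = 10 exposure sessions. At one VR exposure per session, a VR participant has at most 10 in-session CSQ-VR assessments and a TMH participant has 0. Ten is a ceiling, because sessions turn to discussing live exposures once the virtual items are finished and the first live homework is done. Whether VR practice at home also triggers the CSQ-VR is not made clear.

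**The case against.** The strongest reply is that harms are measured more widely than the side-effect gap suggests, and that nothing in the plan depends on comparing them. Much of this stands, and it rules out several stronger readings.

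- A reader might infer that cybersickness is the only harm measured by an instrument. It is not. The DART Risk Assessment Module covers a risk listed in 14.1 in both arms. The anxiety, depression and phobia scales could show worsening in either arm, though the protocol does not designate them as safety measures. Homework anxiety is also solicited by survey in both arms.
- A reader might infer that injuries will certainly go unrecorded. That cannot be known. The homework survey, session notes and data collection forms are held in Local Site Documents, and Figure 2 is not shown. Homework review could also bring an injury to light. The supportable statement is that no collection is stated.
- A reader might infer that the planned analysis will make VR look less safe. Section 16.1 plans no between-arm harm comparison, and safety is not one of its four feasibility benchmarks. The unevenness matters only if side effects are described by arm.
- A reader might take Section 5.4 as denying all further risk. It is limited to risks beyond those usual for this population, and the 14.1 list is introduced as inclusive, not exhaustive.
- Using a VR sickness scale only after VR exposure is reasonable and is not an error.

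What the reply does not remove is that the procedures specify live-animal contact and home headset use, while the risk statements and safety provisions name neither the resulting injuries nor a way to ask about them. Risk listing and harm collection belong in the protocol, so an unseen SAP does not fill this gap.

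**Conclusion.** The point holds as a gap in completeness and ascertainment. Both arms progress to between-session live-animal homework. Animal injury and headset falls or collisions are absent from the listed risks. No adverse-event or injury collection is stated for either arm, and the only treatment side-effect instrument follows VR exposures.

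Its size can be given only as structure: 0 of 7 listed risks concern these injuries, and in-session side-effect assessments number at most 10 per VR participant against 0 per TMH participant. The documents give no injury rate and no number of live exposures, so no count of missed events is offered.

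The conclusion assumes that the forms not shown contain no injury question. If they do, the collection part reduces to stating it in the protocol, and the mismatch between procedures and risk statements remains. This is a cheap improvement; it does not undermine the feasibility benchmarks or the planned ANCOVA.

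**What to change.** Add one brief adverse-event item, worded identically in both arms, to the existing weekly REDCap survey, the homework survey, or both: any injury, allergic reaction, fall or severe distress, answered yes or no with free text. Report it by arm. The weekly survey is sent at the end of each of the 12 therapy sessions, so each arm would have the same 12 scheduled opportunities per participant.

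Reconcile the risk statements in Sections 14.1 and 5.4 with the live-animal homework in Section 4.0 and the home headset use in Section 5.0, and carry the result into the consent text.

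Cost: about a minute per survey. In the weekly survey that is 12 × 1 = 12 minutes per participant. In the homework survey it is at most 6 per week × 12 weeks × 1 = 72 minutes. Both compare with the stated 38 hours or so of participation. The stated risk profile becomes slightly less favourable. No treatment rule changes, and the CSQ-VR can stay as it is.

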5.0 Procedures Involved

This study will use feasibility randomized controlled efficacy trial design. This single-site trial will include up to 60 adults with self-reported fear of dogs, snakes, and/or spiders who will be randomly assigned via the REDCap Randomization Module using a 1:1 allocation ratio to receive 12 sessions of exposure therapy over the course of 3 months via standard telemental health (TMH; $n=15$) vs. Doxy.me VR ($n=15$), a telemedicine-based virtual reality clinic. Participants randomized to the Doxy.me group will be provided with Quest 2 VR headsets with the Doxy.me VR application pre-loaded to the device. This VR clinic is a standalone app currently available on Quest 2 headsets via

invite only. The app is designed for a therapist to meet with a client in a private, comfortable VR clinic office. To join each other in VR, the therapist selects a room code and provides that code to their client, who joins by entering that code into the app. While in the same VR room, the therapist and client can interact by speaking with each other in immersive VR. Therapists can also spawn a variety of small animals such as dogs, snakes, and spiders for use in treating specific phobias. Therapists can browse, select, maneuver, remove, and choose animations for the animals to exhibit once made visible to the client.

Therapy sessions will be audio recorded and 20% will be observed by the PI to assess treatment fidelity. Primary clinical outcomes (i.e., phobia severity as measured by the SMSF) will be assessed at baseline and 3-months post-baseline. Intervention targets will include presence—assessed weekly via patient-report— and working alliance—assessed at mid- and post-treatment via study therapist- and patient-report. Benchmarks for feasibility will include enrolling up to 60 patients during months 1-9 of the trial (i.e., 3/month), 70% patient retention at 3-month follow-up, 70% of weekly self-report collected, and $\geq 80\%$ treatment fidelity.

5.2 Please select the methods that will be employed in this study (select all that apply):

 Audio/Video Recording	 Psychophysiological Recording
 Behavioral Interventions	 Record Review - Educational
 Behavioral Observations and Experimentations	 Record Review - Employee
 Deception	 Record Review- Medical
 Focus Groups	 Record Review - Other
 Interviews	 Specimen Collection or Analysis
 Investigational Device – Non-Significant Risk (e.g. Mobile Applications)	 Surveys and/or Questionnaires
 Psychometric Testing	 Other Social-Behavioral Procedures

Recruitment

Potential participants reached through Clinical Connection, Research Match, and Facebook ads (see Section 12.0 Recruitment Methods) will be provided with a link that will direct them to an Online Pre-Screening Questionnaire that will be administered via a REDCap survey (see Measures in Local Site Documents and Figure 2. Study Schema and Schedule of Events). Potential participants meeting preliminary eligibility criteria will be presented with an invitation to schedule an initial consent and baseline assessment visit via Microsoft Bookings and will receive a calendar invitation and text/email reminders 24 hours and 1 hour prior to the scheduled visit time. If potential participants do not meet eligibility criteria due to participating in ongoing mental health therapy from a non-study therapist or having had changes to psychotropic medication use within six weeks preceding enrollment in the trial, they will be presented with a message inviting them to revisit the pre-screening questionnaire at a later date if/when those conditions no longer apply.

Consent and Baseline Assessment

The consent and baseline assessment visit will be conducted via video-conferencing platform and will not be audio or video recorded. During this visit study staff will (1) confirm the potential participant's responses on the Online Pre-Screening Questionnaire, (2) provide detailed information about the study and explain the informed consent document, (3) assist participants in completing baseline questionnaires via REDCap survey, (4) administer the Specific Phobia and Risk Assessment modules of the Diagnostic Assessment Research Tool (DART; See Measures document for specific items), and (5) make a final determination on the participant's eligibility. Eligible participants will then be randomized using the REDCap Randomization Module and scheduled for their first treatment visit (see Measures in Local Site Documents and Figure 2. Study Schema and Schedule of Events).

Treatment

Participants will receive weekly ≤ 60 -minute therapy sessions (see Section 4.0 Study Intervention). Therapy session visits will be scheduled using Microsoft Bookings and participants will receive a calendar invitation and email reminders 24 hours and 1 hour prior to the scheduled visit time (See Appointment invitations and reminders in Local Site Documents). All therapy sessions will be conducted via videoconferencing, with the Doxy.me VR group transitioning to the Doxy.me VR clinic for the exposure exercise portion of the session. Participants in this group will be mailed a Meta Quest 2 VR headset with the Doxy.me VR app pre-loaded on the device. This headset will be owned by the University of South Florida and will be required to be returned when participants complete the study. Postage will be covered by the study. All therapy sessions will include the assignment of homework, including reading an informational handout after therapy session 1 and exposure therapy assignments after therapy sessions 2-11. Daily exposure-based homework assignments will require participants to practice the same exposure exercises they completed during that week's therapy session for a minimum of 30 minutes, with the specific situation being assigned to participants by the study therapist (i.e., Postdoctoral Fellow). Participants will receive text/email reminders with links to REDCap surveys that will provide instructions for the homework assignment, including situation to be used in the exposure exercise, and ask participants to report the results of the homework exercise including anxiety levels during the exposure exercise (see Treatment Data Collection Forms in Local Site Documents). At the end of each therapy session the study therapist (i.e., Postdoctoral Fellow) will send participants a link via the videoconference platforms messaging feature to a REDCap survey with the weekly assessment, which participants will be asked to complete before the end of the therapy session (see Measures in Local Site Documents and Figure 2. Study Schema and Schedule of Events). Therapy sessions will be audio recorded and 20% of recordings will be observed by the PI to rate fidelity to the protocol. All therapy session notes will be completed and stored in REDCap and signed by both the therapist (i.e., Postdoctoral Fellow) and supervisor (PI).

Assessment Strategy and Measures

All trial assessments are listed in Table 1 and were chosen considering several factors including (1) sound psychometric properties, (2) ease of administration, (3) past use in similar clinical trials, and (4) brevity. All questionnaires will be completed via REDCap

survey with study staff present via videoconference to answer any questions (see Measures in Local Site Documents and Figure 2. Study Schema and Schedule of Events).

[figure not shown]
Table 1. Study Assessments

[figure not shown]
Domain	Informant	Measure
Demographics	Patient	Patient Demographics Questionnaire
Anxiety Severity	Patient	General Anxiety Disorder-7 (GAD-7)(Johnson et al., 2019; Spitzer et al., 2006)
Depression Severity	Patient	Patient Health Questionnaire-9 (PHQ-9)(Kroenke et al., 2011, 2009)
Therapeutic Alliance	Patient Provider	Working Alliance Inventory- Short Revised (WAI-SR)(Hatcher & Gillasp, 2006) Working Alliance Inventory – Short Revised Therapist (WAI-SRT; (Hatcher & Gillasp, 2006)
Treatment Satisfaction	Patient	Client Satisfaction Questionnaire (CSQ-8)(Larsen et al., 1979)
Specific Phobia Severity	Patient	Severity Measure for Specific Phobia-Adult (SMSP-A; (Craske et al., 2013);
Specific Phobia Diagnosis	Patient	Diagnostic Assessment Research Tool (DART;(Schneider et al., 2022)
Presence	Patient	Single Item Presence Questionnaire (SIPQ; (S. Bouchard et al., 2005)
Cybersickness	Patient	Cybersickness in Virtual Reality Questionnaire (CSQ-VR; (Kourtesis et al., 2023)
Usability	Patient	System Usability Scale (Peres et al., 2013)

Treatment Fidelity

All treatment sessions will be recorded and 20% will be rated by the Supervisor (PI) using a Treatment Fidelity Checklist based on the treatment manual (see Treatment Data Collection Forms in Local Site Documents).

Figure 2. Study Schema and Schedule of Events

5.3 There are no procedures or interventions that are going to be conducted as part of this research project that would have been conducted even if the research was not occurring. We are conducting the procedures solely for research purposes.

5.4 There are no additional foreseeable risks to the above procedures in need of further mitigation beyond those ordinarily incurred in working with this population. Standard operational procedures of the USF Department of Psychiatry and Behavioral Neurosciences specify responsibilities for handling dangers to self and others, safety planning, and mandatory reporting responsibilities.

